4.1.1.6 OAR constraints: 5 fraction

MANDATORY (see below):

Spinal cord: Dmax (0.035cc) < 20 Gy Spinal cord + 5 mm: Dmax (0.035cc) < 25 Gy Ipsilateral arytenoid: Dmax (0.035cc) < 43.35 Gy (102% of prescription)

RECOMMENDED:

Uninvolved vocal cord(s): Dmax (0.035cc) <41.4 Gy, Dmean <36.8 Gy Contralateral arytenoid: Dmax (0.035cc) < 23 Gy Ipsilateral carotid: Dmax (0.035cc) <23 Gy, Dmean <11.2 Gy Contralateral carotid: Dmax (0.035cc) <23 Gy, Dmean <11.2 Gy Laryngeal cartilage: Dmax (0.035cc) <46 Gy Cricoid cartilage: Dmax (0.035cc) <41.4 Gy Inferior constrictor and cricopharyngeus: Dmax (0.035cc) <23 Gy Thyroid gland: Dmean <15.3 Gy

4.1.1.7 OAR constraints: 16 fraction

MANDATORY (see below): Spinal cord: Dmax (0.035cc) < 35 Gy Spinal cord + 5 mm: Dmax (0.035cc) < 40 Gy Ipsilateral arytenoid: Dmax (0.035cc) < 61 Gy (105% of prescription)

RECOMMENDED:

Uninvolved vocal cord(s): Dmax (0.035cc) < 56.3 Gy, Dmean <50.05 Gy Contralateral arytenoid: Dmax (0.035cc) < 31.3 Gy Ipsilateral carotid: Dmax (0.035cc) < 31.3 Gy, Dmean <15.2 Gy Contralateral carotid: Dmax (0.035cc) < 31.3 Gy, Dmean <15.2 Gy Laryngeal cartilage: Dmax (0.035cc) < 62.6 Gy Cricoid cartilage: Dmax (0.035cc) < 56.3 Gy Inferior constrictor and cricopharyngeus: Dmax (0.035cc) < 31.3 Gy Thyroid gland: Dmean <20.8 Gy

The standard names for these structures and compliance criteria are below.

Name	Per protocol	Variation acceptable	Variation			
			unacceptable			
PTV	> 95% of PTV	<95%, ≥90% of PTV	< 90%			
	covered by the	covered by prescription				
	prescription dose	dose				
	Max hot spot <115%	>115%, < 120%	> 120%			
IL_arytenoid and	Max hot spot <	Max hot spot < 105% (5	Max hot spot >			
CL_arytenoid	102% (5 fraction)	fraction)	105% (5			
	Max hot spot <	Max hot spot < 108% (16	fraction)			
	105% (16 fraction)	fraction)	Max hot spot <			
			108% (16			
			fraction)			
Cord	< 20 Gy (5 fraction)	>20 Gy, < 25 Gy (5 fx)	> 25 Gy			
	< 35 Gy (16 fraction)	≥35 Gy, < 37.5 Gy (16 fx)	> 37.5 Gy			
Cord_exp	< 25 Gy (5 fraction)	>25 Gy, < 30 Gy (5 fx)	> 30 Gy			
	< 40 Gy (16 fraction)	>40 Gy, < 42.5 Gy (16 fx)	> 42.5 Gy			
OARS	Description See Section 4.1.9.2 for constraints					
VC_uninv	Uninvolved vocal cord and arytenoid, either 1 or both uninvolved					
	vocal cords contoured with a 2 mm separation from PTV					
Carotid_IL	Ipsilateral carotid contoured from the inferior aspect of the hyoid to					
	1 cm below the cricoid					
Carotid_CL	Contralateral carotid contoured from the inferior aspect of the					
	hyoid to 1 cm below the cricoid					
Arytenoid_IL	Ipsilateral arytenoid contoured on the bone window with a 2 mm					
	separation from PTV					
Arytenoid_CL	Contralateral arytenoid contoured on the bone window with a 2					
	mm separation from P	VTV				
Laryngeal_cartilage	Laryngeal cartilage co	ntoured with a 3-5 mm brush	n with a 2 mm			
	separation from PTV					
Cricoid_cartilage	Cricoid cartilage conto	oured with a 3-5 mm brush wi	ith a 2 mm			
	separation from PTV					

STU122017-043, [name], FormA-ResearchProtocol, Mod_29, 02-07-22

Thyroid	Enhancing thyroid gland
IC_CP	Inferior constrictor & cricopharyngeaus contoured from the inferior
	aspect of the hyoid to 1 cm below the inferior aspect of the cricoid

4.1.1.8 Treatment fractionation

5 fraction: Patients will receive one fraction per day, twice per week, with at least two days between fractions.

16 fraction: Patients will receive one fraction per day, 5 days per week

4.1.1.9 Treatment delivery

The CyberKnife machine provides multiple systems that can be used for setting up and imaging patients. The majority of patients in the phase I study were treated with spine tracking, and there were no marginal failures (i.e. no data to suggest the tumors were "missed."); moreover, the spine and larynx are intimately related to each other anatomically.

We also used skin markers for tracking in 2 patients, and it was successful in 1 patient and non-usable in the second patient.

Thus the daily imaging technology will be up to physician discretion. Either spine tracking or skin fiducials may be used.

For treatment with VMAT, daily pre-treatment CBCT must be used for verification of patient set-up and successful treatment delivery with VMAT. At least one intraarc CBCT is mandatory, as is a post-treatment CBCT.

4.1.1.10 Documentation and quality assurance

Every CT simulation scan with target and normal structures will be reviewed by the PI and co-PI.

4.2 Toxicities and Dosing Delays/Dose Modifications

Any subject who receives treatment on this protocol will be evaluable for toxicity. Each patient will be assessed for the development of toxicity according to the Time and Events table in Section 5.4. Toxicity will be assessed according to the NCI Common Toxicity Criteria for Adverse Events (CTCAE), version 4.0.

4.2.1. Radiation Therapy

The dose constraints for radiation therapy are described in 4.1.1.6 and 4.1.1.7. No alterations in treatment doses are allowable per protocol.

4.3 Concomitant Medications/Treatments

Supportive medications may be given at any point during the treatment course at the discretion of the treating physicians. These medications include:

- Anti-emetics
- Non-opiate and opiate pain medications
- Anti-diarrheals

- Nutritional supplementation
- Anti-depressants

The use of anti-oxidant vitamins in excess of a daily vitamin is not allowed.

4.4 Other Modalities or Procedures

For patients receiving 5 fractions, we recommend administering a dexamethasone 4 mg oral tablet one hour prior to each radiation treatment session at the discretion of the treating physician.

4.5 Duration of Therapy

In the absence of treatment delays due to adverse events, treatment may continue until:

- Local, in-field disease progression
- Inter-current illness that prevents further administration of treatment
- Unacceptable adverse event(s)
- Subject decides to withdraw from the study, OR
- General or specific changes in the patient's condition render the subject unacceptable for further treatment in the judgment of the investigator.

4.6 Duration of Follow Up

Subjects will be followed for a minimum of **3 years** after completion of treatment or until death, whichever occurs first. Specifically, subjects will be followed at 1, 3, 6, 9, 12, 18, 24, 30, and 36 months following treatment. Subjects removed from therapy for unacceptable adverse events will be followed until resolution or stabilization of the adverse event.

4.7 Removal of Subjects from Protocol Therapy

Subjects will be removed from therapy when any of the criteria listed in Section 5.5 apply. Notify the Principal Investigator, and document the reason for study removal and the date the subject was removed in the Case Report Form. The subject should be followed-up per protocol.

Patients who are not able to complete the treatment or required follow-up procedures due to cognitive impairment will be removed from the study and treated and/or followed using standard-of-care procedures.

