3.1 Inclusion Criteria

- 3.1.1 Pathologically-proven diagnosis of squamous cell carcinoma *in situ*, squamous cell carcinoma or squamous cell variants (sarcomatoid, verrucous, basaloid, and papillary subtypes) involving the glottic larynx.
- 3.1.2 Clinical stage I-II (AJCC, 7th edition) with direct laryngoscopy showing no evidence of greater than stage II true glottic larynx cancer and PET/CT or CT neck showing no evidence of regional disease.
- 3.1.3 Age \geq 18 years.
- 3.1.4 ECOG Performance Status 0-2
- 3.1.5 Women of child-bearing potential and men must agree to use adequate contraception (hormonal or barrier method of birth control; abstinence) prior to study entry, for the duration of study participation, and for *90* days following completion of therapy. Should a woman become pregnant or suspect she is pregnant while participating in this study, she should inform her treating physician immediately.
 - 3.1.5.1 A female of child-bearing potential is any woman (regardless of sexual orientation, marital status, having undergone a tubal ligation, or remaining celibate by choice) who meets the following criteria:
 - Has not undergone a hysterectomy or bilateral oophorectomy; or
 - Has not been naturally postmenopausal for at least 12 consecutive months (i.e., has had menses at any time in the preceding 12 consecutive months).
- 3.1.6 Negative serum or urine pregnancy test within 2 weeks before registration for women of childbearing potential.
- 3.1.7 Ability to understand and the willingness to sign a written informed consent.
- 3.1.8 Patients with cognitive impairment or other limited decision making capacity with the ability to understand and willingly sign written informed consent or have the consent signed by a designated legally authorized representative (LAR).

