5.3 Follow-up Procedures

Patients will be seen by a radiation oncologist at 1 month (+/- 1 week) and 3 months (+/- 1 week) from the completion of treatment. More frequent visits are encouraged if the patient requires additional help with recovery and rehabilitation

Patients will then be seen every 3 months (+/- 2 weeks) for the first year, and then at least every 6 months (+/-2 weeks) until the end of the 3rd year. Subsequent and intervening follow-up visits will be made per physician preference. These protocol mandated procedures will occur at each follow-up:

- Interim history
- Physical exam, vital signs, ECOG PS (vital signs are not required when patient has a Telehealth visit)
- Laryngoscopy to assess tumor response and toxicity
- Quality of life and voice quality assessment (months 1, 3, 6, 12, 18, 24 and 36)

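### Section 4.7 takes patients who cannot complete study procedures because of cognitive impairment off the study, and nothing provides for recording their later local-control and survival outcomes

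*Combined protocol and SAP*

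**What the plan says.** Sections 3.1.8 and 5.1.1.1 of the combined protocol and SAP allow patients with cognitive impairment to enrol, with a legally authorized representative (LAR) signing where needed. Section 11.2 makes this depend on the investigator judging that the person can get through the study procedures for the whole trial.

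Section 4.7 has two paragraphs. The first covers subjects taken off therapy on any ground in section 5.5, which includes inability to comply (5.5.3). It ends: "The subject should be followed-up per protocol". The second says: "Patients who are not able to complete the treatment or required follow-up procedures due to cognitive impairment will be removed from the study". The consequence in full is that they "will be removed from the study and treated and/or followed using standard-of-care procedures".

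Section 4.6 sets follow-up at no less than 3 years "after completion of treatment or until death, whichever occurs first". Section 5.3 introduces its list with "These protocol mandated procedures will occur at each follow-up". The list holds history, examination, laryngoscopy, and quality-of-life and voice assessment at seven of the visits. Section 5.1.10 and Appendices B to E show that the last item consists of patient-completed forms (QLQ-C30, H&N35, VHI, EQ-5D).

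Section 10.3 names no analysis set, censoring rule or sensitivity analysis for removed patients. Section 4.8 permits replacement only when radiotherapy is not completed.

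**The concern.** A questionnaire and a laryngoscopy serve different endpoints. A patient whose cognition declines may become unable to fill in forms and yet still attend clinic, where the larynx is examined and survival is known. The second paragraph of 4.7 draws no such distinction: it names required procedures as a group, and its consequence is leaving the study, not only stopping therapy.

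Elsewhere the protocol is careful to keep follow-up going. Section 5.5.1 permits it after voluntary withdrawal from treatment, 5.5.2 ends it only when consent is withdrawn, and 5.5.9 asks for two years of documented contact attempts before a subject is called lost. Cognitive decline is not withdrawal of consent, yet 4.7 handles it more like 5.5.2 than 5.5.1.

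At stake are the primary endpoint (2-year local failure), laryngectomy-free survival and overall survival. With 25 patients and few expected failures, one unknown status is visible in the result. Patients removed for this reason may also differ from the rest in their risk of failure or death, so the loss may be informative.

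**Working it through.** **Inputs.** Section 10.2: N = 25; 2-year local control 90% (expected) and 75% (bound); margin 15 points; hazards 0.0527 and 0.1438 per year; ratio 2.73; significance level 0.1; 3 years of accrual plus 2 of follow-up; power above 80%. Section 10.3.1: cumulative incidence, death competing. The number of removed patients, k, is not in the documents; k = 1 to 3 below is illustration only.

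**1. The plan's own figure.**
- Hazards: −ln(0.90)/2 = 0.0527 and −ln(0.75)/2 = 0.1438; ratio 2.73.
- Expected events with uniform accrual and no dropout: O = 25 × [1 − (e^(−2λ) − e^(−5λ))/(3λ)] with λ = 0.0527, which gives 4.19. At the bound hazard, E = 2.73 × 4.19 = 11.43, using the unrounded ratio.
- One-sample log-rank power, one-sided: Φ(|O − E|/√E − 1.282) = Φ(7.25/3.38 − 1.282) = Φ(0.86) = 80.6%.

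This agrees with the stated figure. Section 10.2 does not say whether the test is one-sided; the same formula two-sided gives 69.1%. No allowance for loss is built in.

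**2. Effect on power.** If removed patients contribute nothing, the first term scales by √((25 − k)/25): 79.3% for k = 1, 78.1% for k = 2, 76.7% for k = 3. A simulation of the same design, with removed patients censored at a random time in the first two years, gave 89.3% with none removed and 88.5%, 87.4% and 86.8% for k = 1, 2 and 3. The level depends on the variance form used. The loss is roughly one point per patient either way.

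**3. Effect on the estimate.** At 90% control, 25 × 0.10 = 2.5 failures are expected by 2 years. With f failures among patients of known status and k unknown, true local failure lies between f/25 and (f + k)/25, a width of k/25, or 4 points per patient. For f = 2:

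| k (assumed) | Range | Width |
|---|---|---|
| 1 | 8% to 12% | 4 points |
| 2 | 8% to 16% | 8 points |
| 3 | 8% to 20% | 12 points |

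**4. Direction.** Take one patient lost at the start and a true result of 3/25 = 12.0%.
- If that patient was one of the failures, the observed figure is 2/24 = 8.3%, too low.
- If that patient died without recurrence or stayed controlled, it is 3/24 = 12.5%, too high.

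**5. Likely size.** Suppose removed patients carry twice the design risk (20% against 10%, an assumption). The true rate is then (24 × 0.10 + 1 × 0.20)/25 = 10.4% for k = 1 and (22 × 0.10 + 3 × 0.20)/25 = 11.2% for k = 3, against about 10% observed. That is a bias of 0.4 to 1.2 points.

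**The case against.** Section 11.2 screens at entry for ability to complete procedures, so foreseeable non-completers should not enrol and the rule may never be used. Taking an impaired person out of a study can also be a protection, in keeping with the other safeguards in 11.2. The average bias in step 5 is small against 15 points, and the power loss for one or two patients is minor.

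Three stronger readings are tempting, and the text does not carry them.
- *Data are thrown away.* A reader might infer that existing data are deleted or the patient leaves the analysis. Section 4.7 says neither. That later outcomes go unrecorded follows from leaving the study combined with the absence of any capture provision; it is not an express prohibition.
- *One missed form forces removal.* The text speaks of procedures in the plural and does not mention questionnaires. Section 5.3 makes that reading available but not compulsory.
- *Every endpoint looks too good.* Step 4 shows that local failure can move either way, particularly if removed patients die without recurrence. The documents give no figure linking cognitive decline to outcome.

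What stands against these points: screening at entry cannot exclude later decline, and 11.2 itself anticipates progression of the impairment. Protecting a patient from study procedures does not require ceasing to note recurrence or death from ordinary records. The two paragraphs of 4.7 still treat similar patients differently, and the analysis section is silent on the result.

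**Conclusion.** The point holds as an avoidable and possibly informative loss of primary-endpoint and survival data. Section 4.7 mandates leaving the study where 4.6 and its own first paragraph would keep follow-up going, and no section provides for collecting outcomes afterwards. Its size is 4 points of worst-case uncertainty per affected patient; three such patients would give 12 points against the 15-point margin. Average bias and power loss are probably much smaller.

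This rests on reading departure from the study as the end of study data collection, and on local failure and vital status remaining obtainable in standard care, whose content the protocol does not describe. How many patients are affected is unknown, and the sign of any bias in local failure is not settled. The change is worth making because it costs little, not because the rule as written undermines the design.

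**What to change.** Reconcile the two paragraphs of 4.7 and separate stopping study procedures from stopping outcome collection. Suggested content:
- Unless the patient or LAR withdraws consent, local failure, laryngectomy, grade 3-5 toxicity and vital status continue to be taken from standard-of-care records to month 36 or death.
- These patients stay in the primary and survival analyses; only uncompleted questionnaires count as missing.
- Section 10.3 states how a patient is handled when 2-year status remains unknown, and reports the range in step 3.

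The decision to stop treatment is left exactly as it stands. The new wording must also be squared with 4.8: a patient who does not complete radiotherapy because of cognitive impairment may be replaced, so the plan should say how that patient and the replacement each enter the primary analysis.

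Cost: edits to 4.7 and 10.3, a cross-reference in 4.8, a matching consent sentence, and a small amount of record abstraction, with no added visits. Section 7.2.1 already has the team reviewing radiation oncology, medical oncology and otolaryngology encounters for late adverse events, so the records concerned are largely those already in use.

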4.8 Subject Replacement

Subjects may be replaced in the study if they do not complete radiotherapy. Inadequate receipt of treatment may lead to a higher than expected recurrence rate, and therefore these patients may be replaced. Patient replacement must be verified through review of the case by the P.I.

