5.5 Removal of Subjects from Study

Subjects can be taken off the study treatment and/or study at any time at their own request, or they may be withdrawn at the discretion of the investigator for safety,

behavioral or administrative reasons. The reason(s) for discontinuation will be documented and may include:

- 5.5.1 Subject voluntarily withdraws from treatment (follow-up permitted);
- 5.5.2 Subject withdraws consent (termination of treatment and follow-up);
- 5.5.3 Subject is unable to comply with protocol requirements;
- 5.5.4 Subject demonstrates disease progression (unless continued treatment with study drug/treatment is deemed appropriate at the discretion of the investigator);
- 5.5.5 Subject experiences toxicity that makes continuation in the protocol unsafe;
- 5.5.6 Treating physician judges continuation on the study would not be in the subject's best interest;
- 5.5.7 Subject becomes pregnant (pregnancy to be reported along same timelines as a serious adverse event);
- 5.5.8 Development of second malignancy (except for basal cell carcinoma or squamous cell carcinoma of the skin) that requires treatment, which would interfere with this study;
- 5.5.9 If a research subject cannot be located to document survival after a period of 2 years, the subject may be considered "lost to follow-up." All attempts to contact the subject during the two years must be documented.

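### Section 4.8 allows replacement of patients who do not complete radiotherapy because they may recur more often, and no section says that they stay in the local-failure estimate

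*Combined protocol and SAP*

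**What the plan says.** Section 4.8 (Subject Replacement) makes non-completion of radiotherapy the condition for replacement. The reason is: "Inadequate receipt of treatment may lead to a higher than expected recurrence rate, and therefore these patients may be replaced". The control is: "Patient replacement must be verified through review of the case by the P.I". The section gives no criteria for that review, no cap and no time limit.

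The primary endpoint (2.4.1, 10.1.1, 10.3.1) is the 2-year risk of local failure anywhere in the larynx. Section 10.3.1 specifies only the estimator, cumulative incidence with death as a competing risk. Section 10.2 plans 25 patients without saying who counts towards the 25. Section 4.2 makes every treated subject evaluable, but for toxicity only.

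Treatment can end early in several ways. Section 4.5 lists "Local, in-field disease progression" among its reasons, and 5.5.4 lists disease progression. Section 5.5 also states: "Subjects can be taken off the study treatment and/or study at any time at their own request".

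On follow-up, 4.6 sets a minimum of 3 years for all subjects and adds: "Subjects removed from therapy for unacceptable adverse events will be followed until resolution or stabilization of the adverse event". For patients removed from therapy under 5.5, which includes toxicity (5.5.5), 4.7 says: "The subject should be followed-up per protocol". The exception in 4.7 is for patients who cannot complete treatment or follow-up "due to cognitive impairment will be removed from the study and treated and/or followed using standard-of-care procedures".

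**The concern.** The reason for replacement is the expected value of the primary outcome. Adding a patient does nothing about an inflated recurrence rate unless the replaced patient also leaves the calculation. Read for its purpose, 4.8 therefore leads to an estimate in completers and their replacements only, and nothing in 4.2, 4.7, 10.2 or 10.3.1 prevents this. If non-completers fail more often than completers, as 4.8 itself expects, that estimate is biased downward. For a single patient the direction is not certain, because dropping someone who stays controlled raises the estimated risk.

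The study is small. At 90% control, 25 patients yield 25 × 0.10 = 2.5 expected failures at 2 years, so one or two omitted failures would show. The error that matters most is to declare an inadequate treatment non-inferior. A reader of the final report could not tell which patients had been counted.

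**Working it through.** **Inputs from 10.2.** N = 25; 2-year local control 90% (assumed true) and 75% (margin); log-rank test at 0.1; 3 years of accrual plus 2 years of follow-up.

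**The plan's own figures.** Hazards: -ln(0.90)/2 = 0.0527 and -ln(0.75)/2 = 0.1438, ratio 2.73, as stated. Section 10.2 gives no sidedness and 10.3.1 names no test. I assume a one-sample log-rank test, one-sided 0.10, null hazard 0.1438, uniform accrual and no competing deaths. Success means (E - O)/√E > 1.2816, where O is observed failures and E = 0.1438 × person-years.

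- Expected failures at hazard 0.0527 with 2 to 5 years of follow-up: d = 25 × [1 - (e^(-0.1054) - e^(-0.2634))/(0.0527 × 3)] = 4.19.
- Expected under the null hazard for the same person-years: E = 4.19 × 2.73 = 11.4.
- Power = Φ[(11.4 - 4.19 - 1.2816 × √11.4)/√4.19] = 0.92. Simulation (200,000 trials) gives 0.89.

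This agrees with the stated power of more than 80%. That figure does not depend on the present point. At two-sided 0.10, the wording of the study summary, simulated power is 0.78.

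**Assumed inputs.** k = number of replaced patients restored to the analysis; p = their chance of local failure. The documents give neither, so a range is shown. In the simulation, restored failures occur at 0.1 or 0.5 years, and restored non-failures get full follow-up.

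**Estimate.** With 10% failure in 25 completers, the risk after restoring k patients is (2.5 + k × p)/(25 + k). For example, k = 1 and p = 0.5 gives 3.0/26 = 11.5%.

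| p | Risk, k = 1 | Risk, k = 2 | Net change in success, k = 1 | Net change in success, k = 2 |
|---|---|---|---|---|
| 0% | 9.6% | 9.3% | about +3 points | about +5 points |
| 25% | 10.6% | 11.1% | about 0 | about 0 |
| 50% | 11.5% | 13.0% | about -3 points | about -6 points |
| 100% | 13.5% | 16.7% | about -9 points | about -21 points |

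The last two columns are changes from 0.89. The share of successful trials that turn unsuccessful is about 5% (p = 50%) to 10% (p = 100%) for one restored patient, and about 8-9% to 23-25% for two.

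**Why 25% is roughly neutral for the test.** The null is 25% failure at 2 years, so a restored patient who fails at about that rate adds little evidence either way. The estimate still moves, from 10.0% to 10.6% or 11.1%.

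**Effect on type I error.** Suppose control among all treated patients is exactly 75%. Completers' risk is then [0.25 × (25 + k) - k × p]/25. For k = 1, p = 1 it is (6.5 - 1)/25 = 22%; for k = 2, p = 1 it is (6.75 - 2)/25 = 19%. The simulated one-sided type I error in the 25 completers and replacements rises from 0.087 to 0.11-0.18 (k = 1) or 0.14-0.32 (k = 2), for p from 50% to 100%. If non-completers fail at the completers' rate, there is no bias.

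**The case against.** The strongest reply is that 4.8 never says replaced patients leave the analysis. Replacement is optional, and 4.7 has patients removed from therapy followed per protocol, so their outcomes should exist. A sponsor may also deliberately want the effect of completed SBRT. All of this is fair. It means that the bias is a risk, not a certainty, and that a completers-only result can be reported if it is labelled as such. It does not supply the missing statement of who is analysed.

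The effect is also modest. Treatment lasts about 3 weeks, so few patients may stop, and the loss of success probability is near zero until non-completers fail well above 25%. That stands, and it limits the severity.

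Three stronger readings are tempting, and the documents do not support them.

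- *Patients are replaced because they have recurred.* The trigger is non-completion. Progression can end treatment (4.5, 5.5.4), but no laryngoscopy is scheduled during radiotherapy and, under 6.0, imaging is not used to assess response. This route should rarely occur.
- *Sections 4.6 and 4.7 contradict each other, so 2-year status is lost for patients who stop for toxicity.* The adverse-event sentence in 4.6 reads more naturally as a duty added to the 3-year minimum; 7.2 uses similar language for all adverse events. It is an ambiguity, and harmful only on the less natural reading.
- *The effect on the test is large whatever the failure rate.* Cutting the data at exactly 2 years per patient would enlarge it, but no section states such a cut.

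**Conclusion.** The concern holds as a gap in the definition of the primary analysis. Section 4.8 ties replacement to expected recurrence, and no section keeps replaced patients in the local-failure estimate. If they are dropped, the 2-year risk describes completers only and is biased downward whenever non-completers fail more often. A reader might infer that the protocol orders their exclusion; it only implies it.

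The size cannot be fixed from the documents. In the illustration, one or two restored patients with a 25% to 100% chance of failing move a 10% risk to between 10.6% and 16.7%. The chance of success falls by 0 to 9 points (one) or 0 to 21 points (two). These test figures rest on an assumed one-sided, one-sample log-rank test and the schedule in 10.2. The 21-point figure needs two non-completers who both certainly fail. The change should be made, but the gap does not undermine the design.

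**What to change.** In 4.8 and 10.3.1, state that:

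- the primary analysis includes every registered patient who receives at least one fraction, replaced or not;
- replacement may add patients but never removes one from the analysis;
- local progression during treatment counts as a local failure;
- patients who stop treatment but remain on study are not censored at stopping;
- any patient whose follow-up actually ends, by whichever 5.5 or 4.7 route, is censored at the last laryngeal assessment;
- other local treatment given after stopping is handled in the analysis by a stated rule.

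Report completers only as a labelled sensitivity analysis, with the number of replacements and the reasons. Section 4.7 already has the reason for and date of removal recorded.

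As a minor point, reconcile the adverse-event sentence in 4.6 with the follow-up sentence in 4.7, so that it is clear that 4.6 does not end collection of local-failure status early.

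The cost is a few sentences. Planned sample size, treatment and the option to replace are unchanged. Extra visits arise only if 4.6 is now applied as an early end of follow-up. The estimate may be slightly less favourable, and some of the censoring may be informative.
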